6.3.3 Clinical Laboratory Evaluations

Baseline values are defined as the last measurements taken before the first dose of oliceridine. Change from baseline will be defined as the post baseline value minus the baseline value.

The investigator will exercise his or her medical and scientific judgment in deciding whether an abnormal laboratory finding or other abnormal assessment is clinically significant.

Liver chemistry thresholds have been designed to assure patient safety. When patients meet the hepatic transaminase threshold criteria (AST or ALT $\geq 3 \times$ upper limit of normal [ULN]), the patient should undergo close observation, including monitoring for symptoms (clinical symptoms of hepatitis or hypersensitivity, fatigue, decreased appetite, nausea, vomiting, abdominal pain, jaundice, fever, or rash) and hepatic function (AST, ALT, alkaline phosphatase, and fractionated bilirubin) at least every 48 hours, until symptoms and/or hepatic function abnormalities resolve, stabilize, or return to baseline values. The following thresholds will be derived and presented for hepatic chemistry:

- AST $\geq 3 \times$ ULN
- ALT $\geq 3 \times$ ULN
- AST or ALT $\geq 3 \times$ ULN
- AST $\geq 5 \times$ ULN
- ALT $\geq 5 \times$ ULN
- AST or ALT $\geq 5 \times$ ULN
- BILI $\geq 2 \times$ ULN

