Liver chemistry thresholds have been designed to assure patient safety. When patients meet the hepatic transaminase threshold criteria (AST or ALT $\geq 3 \times$ ULN), the patient should undergo close observation, including monitoring for symptoms (clinical symptoms of hepatitis or hypersensitivity, fatigue, decreased appetite, nausea, vomiting, abdominal pain, jaundice, fever, or rash) and hepatic function (AST, ALT, alkaline phosphatase, and fractionated bilirubin) at least every 48 hours, until symptoms and/or hepatic function abnormalities resolve, stabilize, or return to baseline values. This event must be reported to Trevena within 24 hours of learning of its occurrence.

[Figure 2](#) represents the decision tree for whether or not IP will be discontinued.

Specialist or hepatology consultation should be considered in cases of protocol-mandated IP discontinuation.

Figure 2: Monitoring of Patients with Elevated Hepatic Transaminases

Liver Function Abnormalities

Trevena, Inc.

Protocol CP130-3003

Version 5.0

14 Sep 2016

In addition, every attempt must be made to obtain the following for any patient who meets the hepatic transaminase threshold criteria:

- Viral hepatitis serology including:
 - Hepatitis A immunoglobulin M (IgM) antibody.
 - Hepatitis B surface antigen and hepatitis B core antibody (IgM).
 - HCV RNA.
 - Cytomegalovirus IgM antibody.
 - Epstein-Barr viral capsid antigen IgM antibody (or if unavailable, obtain heterophile antibody or monospot testing).
 - Hepatitis E IgM antibody (if patient resides outside the USA or Canada, or has traveled outside USA or Canada in past 3 months).
- Serum creatine phosphokinase and LDH.
- Record the appearance or worsening of clinical symptoms of hepatitis, or hypersensitivity, fatigue, decreased appetite, nausea, vomiting, abdominal pain, jaundice, fever, or rash, as relevant, on the AE report form.
- Record the use of concomitant medications, including acetaminophen, herbal remedies, other over the counter medications, putative hepatotoxins, or alcohol on the concomitant medications report form.
- The following are required for patients with AST or ALT $\geq 3 \times$ ULN and bilirubin $\geq 2 \times$ ULN but are optional for other abnormal liver chemistries:
 - Anti-nuclear antibody, anti-smooth muscle antibody, and type 1 anti-liver kidney microsomal antibodies.
 - Liver imaging (ultrasound, magnetic resonance, or computerized tomography) to evaluate liver disease.

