8.6.4. Clinical Laboratory Evaluations

All clinical laboratory evaluations will be summarized for the Safety Analysis Set for each cumulative dose group and for all groups combined. Descriptive summaries (mean, SD, median, minimum, and maximum) of absolute values and changes from baseline values will be presented for clinical laboratory values at each time point. Summaries will be performed using the standard units for each analyte. These summaries will be conducted over time using the windows specified in Section 6.2.4.

The number of patients with clinical laboratory values below, within, or above normal ranges for each time point will be tabulated (shift tables) for each clinical laboratory analyte by cumulative dose group.

The proportion of patients who have a clinically significant laboratory result will be summarized by time point for each parameter using frequencies and percentages.

Specific liver-related laboratory results will be summarized by cumulative dose groups and by time point. The specific results summarized will be $AST \geq 3 \times ULN$, $ALT \geq 3 \times ULN$, and AST or $ALT \geq 3 \times ULN$; $AST \geq 5 \times ULN$, $ALT \geq 5 \times ULN$, and AST or $ALT \geq 5 \times ULN$; and $BILI \geq 2 \times ULN$.

For clinically significant and shift summaries, the worst overall value reported will be displayed. These "worst" results will be calculated as the maximum absolute change from baseline.

In addition, laboratory measurements listing will be presented for each patient.

No statistical inference between the treatments will be performed for laboratory evaluations.

Client: Trevena, Inc.
Version #: 1.0
Version Date: 20Dec2016

Protocol/CIP #: CP130-3003

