<T30 Minutes>	xxx (xxx.x)	xxx (xxx.x)	xxx (xxx.x)	xxx (xxx.x)	xxx (xxx.x)	xxx (xxx.x)
Normal	xxx (xxx.x)	xxx (xxx.x)	xxx (xxx.x)	xxx (xxx.x)	xxx (xxx.x)	xxx (xxx.x)
Abnormal, NCS	xxx (xxx.x)	xxx (xxx.x)	xxx (xxx.x)	xxx (xxx.x)	xxx (xxx.x)	xxx (xxx.x)
Abnormal, CSig	xxx (xxx.x)	xxx (xxx.x)	xxx (xxx.x)	xxx (xxx.x)	xxx (xxx.x)	xxx (xxx.x)
Missing	xxx (xxx.x)	xxx (xxx.x)	xxx (xxx.x)	xxx (xxx.x)	xxx (xxx.x)	xxx (xxx.x)
...						

Note: NCS = Not clinically significant; CSig = Clinically significant.

Clinical significance is based on the investigator interpretation as recorded.

Percentages are based on the number of patients with a non-missing baseline and post-baseline windowed time point value within each windowed time point, parameter and cumulative dose group.

Worst post-baseline is calculated as the most extreme absolute change from baseline value.

Trevena, Inc.
Protocol CP130-3003

CONFIDENTIAL
Page x of y

- [a] See section 6.2.3 of the SAP for windowed time point intervals.
- [b] Baseline is the last non-missing value prior to the patient receiving the first dose of oliceridine.

Programmer's Note: Continue with all parameters and all windowed time points even if all counts are 0.

Use the same template as for Table 14.3.3.1.2 for the following tables:

Table 14.3.3.2.2
Clinically Significant Clinical Laboratory Chemistry Results
(Safety Analysis Set)

Table 14.3.4.1
Select Hepatic Laboratory Findings on Treatment
(Safety Analysis Set)

Windowed Time Point [a] Test Result	Oliceridine <= 4 mg N=XXX n (%)	Oliceridine >4 to 8 mg N=XXX n (%)	Oliceridine >8 to 16 mg N=XXX n (%)	Oliceridine >16 to 36 mg N=XXX n (%)	Oliceridine >36 mg N=XXX n (%)	All Treated Patients N=XXX n (%)
Patients with at Least 1 Hepatic Laboratory Finding						
AST >=3 X ULN	xxx (xxx.x)	xxx (xxx.x)	xxx (xxx.x)	xxx (xxx.x)	xxx (xxx.x)	xxx (xxx.x)
ALT >=3 X ULN	xxx (xxx.x)	xxx (xxx.x)	xxx (xxx.x)	xxx (xxx.x)	xxx (xxx.x)	xxx (xxx.x)
AST or ALT >=3 X ULN	xxx (xxx.x)	xxx (xxx.x)	xxx (xxx.x)	xxx (xxx.x)	xxx (xxx.x)	xxx (xxx.x)
AST >=5 X ULN	xxx (xxx.x)	xxx (xxx.x)	xxx (xxx.x)	xxx (xxx.x)	xxx (xxx.x)	xxx (xxx.x)
ALT >=5 X ULN	xxx (xxx.x)	xxx (xxx.x)	xxx (xxx.x)	xxx (xxx.x)	xxx (xxx.x)	xxx (xxx.x)
AST or ALT >=5 X ULN	xxx (xxx.x)	xxx (xxx.x)	xxx (xxx.x)	xxx (xxx.x)	xxx (xxx.x)	xxx (xxx.x)
BILI >=2 X ULN	xxx (xxx.x)	xxx (xxx.x)	xxx (xxx.x)	xxx (xxx.x)	xxx (xxx.x)	xxx (xxx.x)
<T30 Minutes>						
AST >=3 X ULN	xxx (xxx.x)	xxx (xxx.x)	xxx (xxx.x)	xxx (xxx.x)	xxx (xxx.x)	xxx (xxx.x)

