ALT >=3 X ULN	xxx (xxx.x)	xxx (xxx.x)	xxx (xxx.x)	xxx (xxx.x)	xxx (xxx.x)	xxx (xxx.x)
AST or ALT >=3 X ULN	xxx (xxx.x)	xxx (xxx.x)	xxx (xxx.x)	xxx (xxx.x)	xxx (xxx.x)	xxx (xxx.x)
...						

Note: ALT = Alanine Aminotransferase; AST = Aspartate Aminotransferase; BILI = Total Bilirubin; ULN = Upper Limit of Normal.

Percentages are based on the number of patients with a non-missing windowed time point value within each windowed time point and cumulative dose group.

[a] See section 6.2.3 of the SAP for windowed time point intervals.

Programmer's Note: Continue with all windowed time points and criteria rows, even if all counts are 0..

Table 14.3.5.1
Change from Baseline in Vital Signs
(Safety Analysis Set)

Parameter (unit) Windowed Time Point [a]	Baseline/ Observed/ Change from Baseline	Oliceridine						All Treated Patients N=XXX		
		<= 4 mg N=XXX	>4 to 8 mg N=XXX	>8 to 16 mg N=XXX	>16 to 36 mg N=XXX	>36 mg N=XXX				
<Parameter x (unit)>										
<Baseline [b]>										
n	Observed	xxx	xxx	xxx	xxx	xxx	xxx	xxx		
Mean (SD)		xx.x (x.xx)	xx.x (x.xx)	xx.x (x.xx)	xx.x (x.xx)	xx.x (x.xx)	xx.x (x.xx)	xx.x (x.xx)		
Median		xx.x	xx.x	xx.x	xx.x	xx.x	xx.x	xx.x		
Min, Max		xx, xx	xx, xx	xx, xx	xx, xx	xx, xx	xx, xx	xx, xx		
<T30 Minutes>										
n	Baseline [c]	xxx	xxx	xxx	xxx	xxx	xxx	xxx		
Mean (SD)		xx.x (x.xx)	xx.x (x.xx)	xx.x (x.xx)	xx.x (x.xx)	xx.x (x.xx)	xx.x (x.xx)	xx.x (x.xx)		
Median		xx.x	xx.x	xx.x	xx.x	xx.x	xx.x	xx.x		
Min, Max		xx, xx	xx, xx	xx, xx	xx, xx	xx, xx	xx, xx	xx, xx		
n	Observed	xxx	xxx	xxx	xxx	xxx	xxx	xxx		
Mean (SD)		xx.x (x.xx)	xx.x (x.xx)	xx.x (x.xx)	xx.x (x.xx)	xx.x (x.xx)	xx.x (x.xx)	xx.x (x.xx)		
Median		xx.x	xx.x	xx.x	xx.x	xx.x	xx.x	xx.x		
Min, Max		xx, xx	xx, xx	xx, xx	xx, xx	xx, xx	xx, xx	xx, xx		
n	Change	xxx	xxx	xxx	xxx	xxx	xxx	xxx		
Mean (SD)		xx.x (x.xx)	xx.x (x.xx)	xx.x (x.xx)	xx.x (x.xx)	xx.x (x.xx)	xx.x (x.xx)	xx.x (x.xx)		
Median		xx.x	xx.x	xx.x	xx.x	xx.x	xx.x	xx.x		
Min, Max		xx, xx	xx, xx	xx, xx	xx, xx	xx, xx	xx, xx	xx, xx		
...										

[a] See section 6.2.3 of the SAP for windowed time point intervals.

[b] Baseline is the last non-missing value prior to the patient receiving the first dose of oliceridine.

[c] Only patients with both a baseline value and a windowed time point value are summarized at a given windowed time point. *Programmer's Note: Repeat Parameter (unit) in each page if it wraps on to multiple pages.*

Table 14.3.5.2
Change from Baseline in Oxygen Saturation (%)
(Safety Analysis Set)

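### No planned hepatic summary counts patients with AST or ALT ≥3×ULN together with bilirubin ≥2×ULN, and the on-treatment hepatic table does not separate elevations already present at baseline.

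*SAP*

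**What the plan says.** Protocol 4.1.3 sets AST or ALT ≥3×ULN as the threshold for close observation, repeat liver tests, viral serology and rapid reporting to the sponsor. Within that group it marks out a subset: "The following are required for patients with AST or ALT $\geq 3 \times$ ULN and bilirubin $\geq 2 \times$ ULN". The tests in question are autoantibodies and liver imaging, which "but are optional for other abnormal liver chemistries".

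SAP 6.3.3 states "The following thresholds will be derived and presented for hepatic chemistry" and gives seven criteria: AST ≥3, ALT ≥3, AST or ALT ≥3, AST ≥5, ALT ≥5, AST or ALT ≥5, and bilirubin ≥2 (all ×ULN). SAP 8.6.4 says "Specific liver-related laboratory results will be summarized by cumulative dose groups and by time point" and, after "The specific results summarized will be", repeats those seven.

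Mock Table 14.3.4.1, "Select Hepatic Laboratory Findings on Treatment", has one row for each of the seven. Its programmer's note is "Continue with all windowed time points and criteria rows, even if all counts are 0", which repeats the existing rows at each window and adds none. Its percentages are based on patients with a value in the window, with no condition on the baseline value.

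**The concern.** The SAP adopts both cut-offs that make up the protocol's combination but never crosses them. The only combined rows join AST with ALT by *or*; the *and* between transaminase and bilirubin is missing. Safety is the primary objective, so a reader of the hepatic table would want to know how many patients fell in the group for which the protocol requires the fuller work-up. The table as planned does not say.

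The second part concerns baseline. The table's title presents its contents as on-treatment findings, but a patient who enters with ALT ≥3×ULN and stays there is counted in the same row as a patient whose ALT first crosses the threshold after dosing. Without a baseline split, pre-existing disease and new findings are added together.

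**Working it through.** The documents state no expected count or rate for liver abnormalities, so there is no figure to reproduce. The check has three parts.

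**1. Is the joint count reported anywhere in the planned summaries?**

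| Output | What it shows | Joint count? |
|---|---|---|
| SAP 6.3.3, SAP 8.6.4, Table 14.3.4.1 | Seven criteria, bilirubin always alone | No |
| Shift tables (14.3.3.1.1, 14.3.3.2.1) | Low/Normal/High, one analyte at a time | No |
| Clinical-significance tables (14.3.3.1.2, 14.3.3.2.2) | Investigator's interpretation, one analyte at a time | No |
| Listing 16.2.7.1 | Patient-level value and overall interpretation | Only by hand, and no ULN column |

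Protocol 3.6.2.6 uses local laboratories and local ranges, and the study has about 60–90 centers. The mock listing therefore does not give a reader what is needed to turn a value into a multiple of ULN.

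**2. Can the joint count be recovered from the marginal rows?**

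Let N be the patients with data, a the number with AST or ALT ≥3×ULN, b the number with bilirubin ≥2×ULN, and J the number with both. Then

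max(0, a + b − N) ≤ J ≤ min(a, b).

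Take N = 1000 (Protocol 6.1). The values of a and b are assumptions, because the documents give none:

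| a | b | Lower bound | Upper bound |
|---|---|---|---|
| 5 | 5 | 0 | 5 |
| 10 | 10 | 0 | 10 |
| 20 | 10 | 0 | 10 |
| 30 | 20 | 0 | 20 |

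Exact binomial limits at the two ends of the 10/10 case:

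- J = 0: one-sided 95% upper limit 1 − 0.05^(1/1000) = 0.30%; two-sided 95% upper limit 1 − 0.025^(1/1000) = 0.37%.
- J = 10: 10/1000 = 1.0%, Clopper–Pearson 95% interval 0.48% to 1.83%.

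The table is also split by five cumulative dose groups, which tightens the upper bound to the sum over groups of min(a_g, b_g). With small margins the lower bound stays at zero. J is then settled only where one margin is zero, either overall or within every dose group.

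**3. Can an elevation be present at entry?**

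Exclusion 11 (Protocol 3.3.2) joins AST ≥1.5×ULN and ALT ≥1.5×ULN with AND. A patient with raised ALT and AST below 1.5×ULN does not meet it, however high the ALT. Exclusion 13 removes patients whose laboratory abnormality is judged clinically significant, but it carries no numeric limit. An isolated ALT elevation judged not significant can therefore enter. The shift tables do carry a baseline category, but High means above the normal range. A patient moving from 1.2× to 4×ULN and one staying at 4×ULN both appear as High to High.

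**The case against.** The strongest reply is that nothing is lost. AST, ALT and bilirubin are on the same chemistry panel, and the flags for each component must be derived anyway for the seven rows, so the joint count could be produced from the database at any time. SAP 8.6.4 also promises that a "laboratory measurements listing will be presented for each patient". Every AST or ALT ≥3×ULN event goes to the sponsor within 24 hours, so each joint case sits inside an individually reported group. Clinically significant abnormalities that meet the AE definition are tabulated as AEs. The study is descriptive, with no inference on laboratory data, and has only one scheduled post-baseline laboratory draw.

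Most of this stands, and it rules out the stronger reading that combined cases cannot be counted or would go unnoticed. It does not put the count into a pre-specified table. A count derived later would also leave the definition of a case to be chosen after the data are seen. For a patient with a single post-baseline sample, same-sample and any-time rules agree. They can differ for patients with repeat samples, and those are the patients the protocol follows with repeat liver tests.

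A reader might also infer that the protocol labels the combination as more serious. It does not use that term; it makes further tests mandatory for this group, and the decision-tree figure is not available in the text reviewed.

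On baseline, exclusion 13 narrows the route, and the change-from-baseline, shift and clinical-significance tables do carry baseline information. The documents give no rate for isolated ALT elevation at entry, so it should not be presented as common or tied to a particular diagnosis. What remains is that no planned table shows baseline status at the 3×ULN cut.

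**Conclusion.** The point holds as a reporting gap in the planned hepatic summaries. The combination that Protocol 4.1.3 singles out for required work-up has no row in SAP 6.3.3, SAP 8.6.4 or Table 14.3.4.1, and the marginal rows determine it only when one margin is zero. On the assumed margins of 5 to 30, the unresolved range is 0 up to between 5 and 20 patients per 1000; these are illustrations and not forecasts. Table 14.3.4.1 also mixes pre-existing with new elevations. How much this matters depends on how many patients enter above a threshold, which the documents do not allow one to estimate.

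The gap affects no sample size, power or error rate. The change is worth making because safety is the primary objective and the cost is very small.

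**What to change.** - Add a patient-level criterion, AST or ALT ≥3×ULN and bilirubin ≥2×ULN, to SAP 6.3.3, SAP 8.6.4 and Table 14.3.4.1, overall and by time point.
- State in advance whether both parts must be met in the same sample or at any post-baseline time.
- Show each hepatic row also for patients who were below that row's threshold at baseline, with that group as the denominator.
- Add the site ULN, or the value as a multiple of ULN, to Listing 16.2.7.1.

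The cost is a few derived flags, some extra table rows and one listing column. All of it comes from data already collected, with no new assessments and no change to clinical management.

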6.3.4 Vital Signs

Baseline values are defined as the last measurements taken before the first dose of oliceridine. Change from baseline will be defined as the post baseline value minus the baseline value. Vital signs will include blood pressure (BP), heart rate (HR), respiratory rate (RR), and temperature. Temperature will be measured at screening and baseline only.

Potentially clinically significant abnormal (PCSA) vital signs parameter criteria is defined below:

Parameter	Criterion value	Change relative to baseline
Systolic blood pressure (mmHg)	≥ 180 mmHg	25% increase
Systolic blood pressure (mmHg)	≤ 80 mmHg	25% decrease
Diastolic blood pressure (mmHg)	≥ 110 mmHg	25% increase
Diastolic blood pressure (mmHg)	≤ 40 mmHg	25% decrease
Pulse rate (bpm)	≥ 120 bpm	15 bpm increase
Pulse rate (bpm)	≤ 40 bpm	15 bpm decrease

Client: Trevena, Inc.
Version #: 1.0
Version Date: 20Dec2016

Protocol/CIP #: CP130-3003

6.3.5 Electrocardiogram (ECG)

ECG summaries will include HR, PR interval, RR interval, QRS interval, QT interval, and QTcF interval. Baseline values are defined as the last measurements taken before the first dose of oliceridine. Change from baseline will be defined as the post baseline value minus the baseline value.

In addition to the observed values for these parameters, the following will be categorized:

- Change from Baseline QTcF > 30 milliseconds
- Change from Baseline QTcF > 60 milliseconds
- Increase of QTcF to > 500 milliseconds

The investigator will exercise his or her medical and scientific judgment in deciding whether an abnormal finding is clinically significant.

6.3.6 Physical Examination

The physical examination will include general appearance. Results from screening/baseline will be recorded as medical history events while changes from screening/baseline in the physical examination will be recorded as AEs. The investigator will exercise his or her medical and scientific judgment in deciding whether an abnormal finding is clinically significant.

6.3.7 Subjective Opiate Withdrawal Scale (SOWS)

The Subjective Opioid Withdrawal Scale (SOWS) will be administered one day after completion of the treatment phase to detect symptoms of opioid withdrawal. Patients will score each of the 16 symptoms on an intensity scale ranging from 0 “not at all” to 4 “extremely”.

If the patient is discharged or transferred before the time when the SOWS is to be performed, it will be performed one day after completion of the treatment phase and returned to the site by mail or in person.

Each patient should have exactly one SOWS administered during the study. However, if multiple SOWS results are collected for any given patient, the record with the most extreme total score will be used for summary purposes.

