3.5.2.3 Dosing Limit

For the current study, the dosing limit for oliceridine will be 60 mg in the first 12 hours. If a patient reaches this dosing limit within the first 12 hours, a PK sample will be obtained, the patient will early discontinue oliceridine and will be managed conventionally.

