3.5.5 Permitted and Prohibited Prior and Concomitant Medications

Prior medications are defined as those taken before the first dose of oliceridine. Concomitant medications are defined as those taken after the first dose of oliceridine.

Concomitant non-opioid analgesics are permitted. If a concomitant parenteral or oral opioid analgesic is used during the treatment phase, oliceridine treatment will cease, and the patient will be discontinued early and will undergo the end-of-treatment phase and follow-up phase procedures as scheduled.

Unless specifically prohibited, other medications are permitted, including common treatments of opioid-related adverse effects (eg, antiemetics, antacids, stool laxatives) and medications used to treat underlying medical conditions.

As with conventional opioids, prior and concomitant use of anxiolytics, sedative-hypnotics, or other potential CNS depressants requires elevated vigilance, consistent with the Joint Commission Sentinel Event Alert for the safe use of opioids in hospitals ([The Joint Commission, 2012](#)). Similarly, the perioperative use of epidural or intrathecal opioids prior to oliceridine requires cautious administration and increased monitoring, consistent with the American Society of Anesthesiologists Task Force on Neuraxial Opioids and the American Society of Regional Anesthesia and Pain Medicine Practice Guidelines for the Prevention, Detection, and Management of Respiratory Depression Associated with Neuraxial Opioid Administration ([American Society of Anesthesiologists 2016](#)).

Supplemental oxygen will be recorded as a prior and/or concomitant medication.

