8.3.2. Safety Analysis Set

The safety analysis population will include all enrolled patients receiving at least 1 dose of oliceridine.

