8.6 Analysis of Safety

The Safety Analysis Set will be used for all safety summaries. Summaries will be tabulated by cumulative dose group and for all groups combined.

Client: Trevena, Inc.
 Version #: 1.0
 Version Date: 20Dec2016

Protocol/CIP #: CP130-3003

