8.6.8. Subjective Opiate Withdrawal Scale (SOWS)

SOWS total score will be summarized with descriptive statistics (number of patients [N], mean, standard deviation [SD], median, minimum, and maximum) for the Safety Analysis Set. All SOWS results will also be listed by treatment.

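### The single post-treatment SOWS is summarized over all dosed patients without separating those given another opioid beforehand, so a low mean does not by itself support absence of withdrawal

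*SAP*

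**What the plan says.** SAP 6.3.7 gives the scale its timing and purpose: it "will be administered one day after completion of the treatment phase to detect symptoms of opioid withdrawal". Each patient is expected to have one assessment. The schedules of events show no pre-treatment SOWS, and SAP 6.2.1 does not list it among the assessments with a baseline value.

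On analysis, SAP 8.6.8 states that "SOWS total score will be summarized with descriptive statistics", ending with "median, minimum, and maximum) for the Safety Analysis Set". SAP 8.3.2 defines that set: "The safety analysis population will include all enrolled patients receiving at least 1 dose of oliceridine". For safety tables in general, SAP 8.6 says: "Summaries will be tabulated by cumulative dose group and for all groups combined". Mock Table 14.3.8.1 follows this layout, with five dose-group columns and one for all treated patients. The subgroups in SAP 7.7 are sex, age, race, baseline NPRS, initial setting, BMI and CYP2D6 status. Opioid use after oliceridine is not among them, and SAP 7.3.6 deals only with missing SOWS items.

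On other opioids, Protocol 3.5.5 says: "If a concomitant parenteral or oral opioid analgesic is used during the treatment phase, oliceridine treatment will cease". Such a patient is discontinued early but "will undergo the end-of-treatment phase and follow-up phase procedures as scheduled". The schedule places the SOWS in the end-of-treatment phase, so these patients are due to be scored. For a patient who reaches the dosing limit, Protocol 3.5.2.3 says "the patient will early discontinue oliceridine and will be managed conventionally", without naming the later analgesic. Neither document restricts opioids between the end of treatment and the SOWS.

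**The concern.** The scale is there to detect opioid withdrawal. A patient who has moved to another opioid before the assessment may have few withdrawal symptoms because of that opioid, whatever oliceridine would have left behind. Averaging such patients with those who stopped all opioids pulls the mean toward no withdrawal, which is the reassuring direction in a study whose primary objective is safety.

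The dose-group columns do not remove this, because the share on another opioid may differ between groups. The most heavily exposed patients include those who stopped at the dosing limit, and their later analgesia is unspecified. At stake is what can be concluded from a low SOWS mean: as planned, a reader cannot tell little withdrawal from much opioid cover.

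**Working it through.** The documents state no SOWS threshold, expected score or share of patients on other opioids, so there is no planned figure to reproduce. The check asks how much of a true excess would survive pooling.

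**Inputs from the documents:** about 1000 treated patients (SAP 4.4); SOWS range 0 to 64 (SAP 7.3.6); summary over all dosed patients (SAP 8.6.8).

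**Assumed inputs:**
- f, the share of patients on another opioid at the SOWS: 10% to 90%.
- m, the degree to which that opioid suppresses the withdrawal excess: 1 (complete) or 0.5 (half).
- d, the true mean excess due to withdrawal in opioid-free patients: 8 points, for illustration.
- Background symptoms are the same in both groups.

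**Formula:** pooled excess = (1 − f) × d + f × (1 − m) × d = d × (1 − f × m).

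| f | Kept, m = 1 | 8 points appear as | Kept, m = 0.5 | 8 points appear as |
|---|---|---|---|---|
| 10% | 90% | 7.2 | 95% | 7.6 |
| 25% | 75% | 6.0 | 87.5% | 7.0 |
| 50% | 50% | 4.0 | 75% | 6.0 |
| 75% | 25% | 2.0 | 62.5% | 5.0 |
| 90% | 10% | 0.8 | 55% | 4.4 |

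**Dose groups.** Take complete masking and assumed true excesses of 2 points at low dose with f = 25%, and 6 points at high dose with f = 75%. The table would show 2 × 0.75 = 1.5 and 6 × 0.25 = 1.5. A threefold gradient would disappear.

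**Information left after a split.** With 1000 patients and SOWS complete in all of them, the opioid-free group has n = 1000 × (1 − f). If no withdrawal case is seen, the exact one-sided 95% upper bound on the rate is 1 − 0.05^(1/n):
- n = 900: 0.33%
- n = 750: 0.40%
- n = 500: 0.60%
- n = 250: 1.19%
- n = 100: 2.95%

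Counting all 1000 as informative would give 0.30%.

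**Individual cases.** If withdrawal truly occurs in 1% of opioid-free patients, the chance of at least one case is 1 − 0.99^n: 99.3% at n = 500, 91.9% at n = 250 and 63.4% at n = 100.

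**The case against.** The strongest reply is that the plan offers more than one pooled mean. SOWS is shown by five dose groups as well as overall, with SD, median, minimum and maximum. Listing 16.2.9 gives each symptom score with date and time, and Listing 16.2.2.2 gives medication start and stop times, so a high score can be read against a patient's opioid use. Protocol 3.6.2.7 also has patients monitored for signs and symptoms of withdrawal, and adverse events are recorded to the follow-up phase. This stands. A reader might infer that the pooled score cannot show withdrawal at all; the documents do not support that. Individual cases could surface, and the loss in the mean is partial and of unknown size.

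A second reply is that the premise is partly inference. This also stands. Use of another opioid is certain by design only for patients who switched during treatment. For the rest it is permitted but not stated, and no passage says that another opioid lowers the SOWS. A reader might infer that most patients will be covered, so that nearly all the signal is lost; that takes only the unfavourable end of the range.

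Third, a reader might infer that the sponsor will report an absence of withdrawal. The SAP plans descriptive statistics only, with no threshold, test or stated conclusion for SOWS.

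Fourth, splitting by opioid use leaves the missing baseline untouched. Items such as nausea, aches, anxiety and restlessness can come from the surgery or illness itself, and the opioid-free patients are self-selected. That is correct and limits what the split can deliver. It is not a reason to keep the undivided summary as the only one, since cross-reading listings patient by patient is no substitute for a prespecified table.

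**Conclusion.** The point holds as one of dilution and interpretation. The plan combines patients with and without an intervening opioid in its only SOWS summary, although the protocol itself expects some patients to have switched. If replacement opioids suppress withdrawal symptoms, the mean understates withdrawal in those who stopped opioids. The understatement is small if few patients are covered or masking is weak (7.2 or 7.6 of 8 points kept at f = 10%) and severe if most are covered and masking is complete (0.8 of 8 points at f = 90%). The share, the degree of masking and the 8-point excess are all assumptions; the documents give none of them.

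What follows is that a low all-patient score does not by itself support absence of withdrawal. It does not follow that the scale is uninformative, or that a false conclusion is planned. This is a cheap improvement to the analysis, not a flaw that threatens the study.

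**What to change.** In SAP 8.6.8 and Table 14.3.8.1:
- Keep the all-patient summary.
- Add the same statistics for patients with and without any opioid between the last oliceridine dose and the SOWS, counting an opioid started earlier and still ongoing.
- Show n in each group by cumulative dose group and by treatment duration.
- Read any statement about withdrawal from the opioid-free group. Note beside it that this group is smaller and self-selected and that SOWS has no baseline, so the split reduces the problem without giving an unbiased estimate.
- State a rule for missing times. SAP 7.3.2 imputes a missing medication start time only on the date of the first dose, so ordering on the day of the last dose or of the SOWS is undefined. One option is to count unresolved cases as opioid-exposed and report how many there are.

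The data are already collected: concomitant medications are recorded through the follow-up contact (Protocol 3.1.6), and the SOWS form carries its own date and time. The cost is one derived flag, one timing rule and some extra columns. Some classifications will be uncertain, because SOWS may be returned by mail and follow-up may be by telephone. The flag also counts any opioid since the last dose, which is broader than being on one at the moment of the SOWS; that keeps the opioid-free group clean but shrinks it. No new assessment and no change to patient care is involved.
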